## **13.0 DESCRIPTION OF OUTCOMES AND VARIABLES**

### **Primary outcome**

Change in antibody levels to influenza virus strains included in the IIV, comparing levels at day 14 and day 42; just before and 4 weeks after influenza vaccination (for group 4, it will be 2 and 6 weeks after influenza vaccination).

We will use *Influvactetra* (Mylan ApS, Copenhagen), a quadrivalent inactivated influenza vaccine containing the following strains:

1. A/Victoria/2570/2019, IVR-215 (H1N1, pdm09-like strain)
2. A/Cambodia/e0826360/2020, IVR-224 (H3N2-strain)
3. B/Washington/02/2019, wild type
4. B/Phuket/3073/2013, wild type

Influenza antibodies are measured in hemagglutination-inhibition assay (HAI) yielding dilution titers with an expected range of <20 to 320 for this population. Geometric mean titers (GMT) will be determined by calculating the mean of the log-transformed duplicate titers followed by back transformation (calculated as  $10^x$ , where x is defined as the mean log-transformed titer).

Seroconversion is defined as a pre-vaccination HAI titer <10 and a post-vaccination titer  $\geq 40$ , or a pre-vaccination titer  $\geq 10$  and a minimum four-fold rise in post-vaccination titer.

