## 10.0 STUDY METHODS

### Trial design

A single-blinded, placebo controlled, randomized clinical trial, with nested immunological studies. Participants are randomized 1:1:1:1 to four groups: BCG 14 days before, together with, or 14 days after IIV compared to placebo.

People  $\geq 65$  years of age who plan to accept the offer of seasonal influenza vaccination are eligible for participation.

Participants are vaccinated once at day 0 and twice at day 14 (one shot in each arm). All participants receive the standard seasonal IIV recommended by the Danish Board of Health. The participants will come back for a follow-up interview at day 42 and all are followed for six months post-randomization with electronic questionnaires about their health. These include information on symptoms and disease, potential side effects, other vaccinations, visits to general practitioner or on call doctor, and hospitalizations. Every survey period is 14 days, starting from day 0 (inclusion).

Blood samples for influenza antibody testing are collected from all participants at day 14 and 42. Samples for further immunological analyses are collected from subgroups at day 0, day 14, day 21, and day 42.

Vaccination schedule:

Group	Day 0 (one shot)	Day 14 (two shots)	Day 42
1	BCG	IIV + Placebo	Follow up visit
2 (Control)	Placebo	IIV + Placebo	Follow up visit
3	Placebo	IIV + BCG	Follow up visit
4	IIV	Placebo + BCG	Follow up visit

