For the trained immunity analyses, 15 participants from each group will have extra blood samples taken on day 0, 14, and 42. Peripheral blood mononuclear cells (PBMCs) are isolated from the samples and subsequently stimulated in vitro with various antigens. The immune function will be assessed by cytokine production capacity measured by Luminex technology after stimulation. The outcome measure for this analysis is concentration of different types of cytokines produced following stimulations. We will compare fold change in cytokine production between the groups at the various timepoints with and without adjustment for responses in control medium. This will allow us to determine whether BCG in the different combinations with influenza vaccine induces trained immunity in this population.

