**List of variables:**

Variable name	Definition	Type	Scale
Primary outcome: Change in antibody levels to influenza virus strains included in the IIV, comparing levels at day 14 and day 42.			
ab_diff_strain	Influenza antibody titer (GMT) day 42 minus day 14. For each strain.	Continuous	<20 to 320
seroconv	Seroconverted after influenza vaccination (4-fold increase in Ab titer). For each strain.	Binary	0: no 1: yes
Secondary outcome, self-reported infections:			
infection	Infection or symptoms consistent with infection (0 or 1 every survey period).	Binary	0: no 1: yes
Secondary exposure:			
ab_day42_cat	Influenza ab titer day 42 (GMT). Secondary exposure.	Categorical	1. quartile 2. quartile 3. quartile 4. quartile
Secondary outcome, immunological:			
b_lymph	Number of activated B-cells. For all relevant subtypes.	Continuous	0.0-0.3 x 10  /L

cytokine_stim_day	Cytokine concentration (TNF $\alpha$ , IL-1 $\beta$ , IFN- $\gamma$ ) after stimulation with: Poly(I:C), Pam3CSK4, LPS, and influenza vaccine at the various timepoints (day 0, 14, and 42).	Continuous	0-1500 pg/mL
diff_cytokine_stim_day	Fold change in cytokine concentration from baseline value (day 0) to day 14 and 42 after stimulation with various stimuli. Compared between the randomization groups. Using randomization group as exposure (categorical).	Continuous	0-10

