#### Primary outcome:

Mean change in GMT in samples from day 14 and 42 will be compared between the control group and the three treatment groups in linear regression analyses with adjustment for baseline level of GMT, age group, and sex. In case residuals are not normally distributed, the analysis will be performed on log-10 transformed change in GMT instead. The proportion of participants who seroconvert will be compared in logistic regression analysis with adjustment for age group and sex.

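### Part B: group 4 has no pre-vaccination antibody sample, so its seroconversion and day 14–42 comparisons with control cannot be read as a BCG effect

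*SAP*

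**What the plan says.** The Part B schedule (section 10.0, Trial design) gives IIV on day 14 to groups 1, 2 (control) and 3, and on day 0 to group 4, which receives BCG on day 14. On sampling it says: "Blood samples for influenza antibody testing are collected from all participants at day 14 and 42".

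Section 13.0, Primary outcome, states the resulting timing openly: "for group 4, it will be 2 and 6 weeks after influenza vaccination". It then sets the binary measure: "Seroconversion is defined as a pre-vaccination HAI titer <10 and a post-vaccination titer" of at least 40, or a four-fold rise from a pre-vaccination titre of 10 or more. The list of variables defines the continuous measure as "Influenza antibody titer (GMT) day 42 minus day 14. For each strain".

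Section 14.0 says "Mean change in GMT in samples from day 14 and 42 will be compared between the control group and the three treatment groups", "with adjustment for baseline level of GMT, age group, and sex". The scale depends on a residual check: "In case residuals are not normally distributed, the analysis will be performed on log-10 transformed change in GMT instead". Seroconversion is compared by logistic regression, with no exception for group 4. Table 2 reserves a β and an odds ratio for group 4 in each of the four strains, and hypothesis (a) in section 2.0 covers all three BCG timings.

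The only day 0 blood is in a subset: "For the trained immunity analyses, 15 participants from each group will have extra blood samples taken on day 0, 14, and 42". It is planned for cell stimulation and cytokines; no HAI test on it is mentioned. For the B-lymphocyte analysis, section 13.0 leaves group 4 out because its IIV date differs.

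**The concern.** The timing is disclosed, but no analysis rule follows from it. The SAP accepts for the B-lymphocyte analysis that group 4 is not comparable on this calendar, yet keeps it in the primary comparison, where the same reason applies.

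Two things go wrong. Seroconversion in group 4 cannot be determined as defined; if the day 14 titre is used instead, it is measured against a level that IIV may already have raised. The change in titre covers weeks 0 to 4 after IIV in control and weeks 2 to 6 in group 4, and the baseline covariate is pre-vaccination in one and post-vaccination in the other. No group receives IIV on day 0 without BCG, so nothing in the data separates timing from BCG.

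At stake is one of the three primary contrasts: 4 of the 12 β values and 4 of the 12 odds ratios in Table 2 (3 contrasts × 4 strains). They would be printed beside valid ones and read as evidence for or against BCG given two weeks after IIV.

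**Working it through.** **1. Timing, from the schedule in section 10.0** (sampling day minus IIV day).

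| Group | IIV day | First sample | Second sample |
|---|---|---|---|
| 1, 2, 3 | 14 | 14 − 14 = 0 days | 42 − 14 = 28 days (4 weeks) |
| 4 | 0 | 14 − 0 = 14 days (2 weeks) | 42 − 0 = 42 days (6 weeks) |

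This reproduces the SAP's own figures.

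**2. Seroconversion.** Both limbs of the definition need a pre-vaccination titre. Group 4 has none among the planned HAI samples. Day 0 blood exists for 15 of 75 (20%), for another purpose. There is also a ceiling: with the stated upper range of 320, a four-fold rise needs a starting titre of at most 320/4 = 80. A group 4 participant already above 80 on day 14 cannot show it within that range, however well IIV worked.

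**3. Change in titre, log scale, no BCG effect.** Let *b* be the mean pre-IIV log titre, *r* the mean rise by week 4, *f* the fraction of the rise present by week 2, and *d* the shift from week 4 to week 6.

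- Control: (b + r) − b = r.
- Group 4: (b + r + d) − (b + f·r) = (1 − f)·r + d.
- Group 4 minus control: d − f·r.

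Adjusting for the day 14 titre with slope β gives d − f·r − β·f·r = d − f·r(1 + β). The *f·r* term vanishes only if β = −1, and *d* remains even then. Adjustment is not a cure.

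The SAP gives neither *f* nor *d*. In the simulation below, 50% control seroconversion (section 10.0, Sample size) corresponds to r = 1.7–2.7 log2. Before adjustment, and ignoring assay limits, the bias is:

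- f = 0.5, d = 0: −0.85 to −1.35 log2.
- f = 0.25, d = 0: −0.43 to −0.68.
- f = 0.25, d = +0.5: −0.18 to +0.08.
- f = 0.1, d = +0.3: +0.03 to +0.13.

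**4. Apparent group 4 seroconversion, day 14 used as the starting titre, no BCG effect, control 50%.** The simulation used 108 assumed settings: baseline geometric mean 10, 14 or 20; baseline SD 1.0 or 1.4 log2; SD of rise 0.8, 1.2 or 1.6; measurement SD 0.4; cap at 320; three ways of reading the dilution step; values below 20 read as 10 or not. Each setting had 100,000 subjects.

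| | d = −0.3 | d = 0 | d = +0.3 | d = +0.5 |
|---|---|---|---|---|
| f = 0.25 | 17.5–37.3% | 27.5–44.7% | 39.3–53.2% | 44.1–60.7% |
| f = 0.5 | 2.9–21.5% | 7.1–30.3% | 13.9–39.9% | 20.6–46.5% |

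At f = 0.1, d = +0.3 it is 50.5–58.4%. A separate simulation with a faster assumed response (50–100% of the rise by week 2, week 6 level 90–100% of week 4) gave 0–11%.

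**5. False findings with the planned models.** Five of these settings, 68 per group (75 × 0.9 = 67.5), 1,000 null trials each. The logistic model called group 4 significantly lower in 19–63% of trials at f = 0.25, d = 0 and in 90–100% at f = 0.5, d = 0. At f = 0.1, d = +0.3 it called group 4 higher in 5–12%.

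**6. Groups 1 and 3.** Their timing matches control. If one linear model holds all four groups, group 4 still enters the shared baseline slope and residual variance. At f = 0.5, d = 0 on change in log titre, this shrank group 1's standard error by 5.5–7.5% and put its type I error at 5.9–9.0%, against 4.0–6.1% without group 4. On the titre scale the figures were 4.9–7.9% against 4.1–6.1%. Repeat runs gave 6.2–7.5% with group 4 in the fit, so the 9% end should not be relied on.

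**The case against.** - **Seroconversion can be computed.** The list of variables describes it simply as a four-fold increase, which an analyst could take between days 14 and 42. That is true, but the result does not meet the definition in section 13.0 and is not the same quantity as in control.
- **It is a disclosed design feature.** Day 14 is also when group 4 receives BCG, so days 14–42 are its post-BCG interval. This stands: the missing element is a control with IIV on day 0, which the SAP cannot supply. Disclosure still does not make the planned contrast interpretable.
- **The sizes come from assumed kinetics.** This stands. They show that the bias can be large and can run either way, not what it will be.
- **The effect on groups 1 and 3 is conditional and small.** This also stands. Section 14.0 does not say whether one model or pairwise models are meant. The simulated log analysis uses change in log titre, whereas the SAP's fallback reads literally as the log of the change. The main point does not depend on this part.
- **Removing an arm from the primary outcome touches a stated hypothesis.** That is fair, and it has to be said openly in the plan; the protocol, not available here, may need a matching statement.

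**Conclusion.** The concern holds. From the SAP's own schedule and definitions, group 4's seroconversion is undefined as written, and its day 14–42 change is not comparable with control. One of three primary contrasts cannot test the part of hypothesis (a) about BCG two weeks after IIV. This conclusion needs no assumption about kinetics.

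Only the direction and size do. With no BCG effect, the bias is downward if part of the rise is present by week 2 and titres have levelled off or fallen by week 6; it can turn upward if titres keep rising after week 4. The contrasts of groups 1 and 3 with control have valid timing; any spill-over into them requires a joint four-group model and is modest. The plan must be corrected before the Part B primary analysis is run.

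**What to change.** - **Section 13.0, Primary outcome:** state that day 14–42 change and seroconversion are defined for groups 1–3 only, because group 4 has no pre-IIV HAI sample. Add the same restriction to *ab_diff_strain* and *seroconv* in the list of variables.
- **Section 14.0:** compare groups 1 and 3 with group 2 in models fitted to groups 1, 2 and 3 only, leaving group 4 out of the baseline slope and the residual check.
- **Table 2:** mark the group 4 β and odds-ratio cells *not applicable*.
- **Group 4:** report separately, as a secondary comparison, the difference from group 2 in day-42 log10 titre with 95% CI, with sex and age-group terms but without the day 14 titre. Label it *6 versus 4 weeks after IIV* and do not interpret it as a pure BCG effect.
- **Section 2.0:** say that the day 14–42 endpoint does not test the two-weeks-after-IIV part of hypothesis (a).

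The cost is wording in the SAP and its tables; no new data are needed, and each remaining pair keeps 75 planned participants per group. Group 4 loses its formal primary contrast. Its day-42 comparison still differs from control by two weeks since IIV: with no BCG effect it was significant in 4–5% of simulated trials at d = 0, but in 14–24% at d = −0.3 and 26–54% at d = +0.5, which is why the label is needed.

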### **Secondary outcomes**

*Self-reported infections:*

Infections are identified through information given by the participants in the electronic follow-up questionnaires, where they are asked to describe disease episodes every 14 days. They are asked if they have been ill, and then asked to cross off their symptoms on a list. Furthermore, we ask them to provide the most likely cause for their illness. Disease episodes are characterized as infections if participants report symptoms compatible with an infectious disease or they report an infectious disease diagnose as the cause of their illness. Criteria for self-reported infection:

- Having one or more of the following symptoms: fever, cough, sore throat, runny nose/nasal congestion (common cold symptoms), loss of smell or taste sense, vomiting, or diarrhea with or without general symptoms such as headache, myalgia, dysarthria, or fatigue.
- Having dyspnea AND fever with or without general symptoms such as headache, myalgia, dysarthria, or fatigue.
- Having described an infectious disease as the self-estimated cause of illness. This is a free-text field and participants answers will be classified as infectious disease or not by medically trained study personnel.

Baseline for analysis is set at day 14 reflecting completion of the allocated vaccinations. We will however also conduct the analysis from day 0-14. Participants can register a maximum of one infectious disease event per survey period (14 days).

A secondary analysis of association between influenza antibody level and subsequent risk of infection will be performed to test if high antibody titers correlate with risk of infection.

*Immunological outcomes (subgroup analyses):*

A random subset of participants (the first to accept) have extra blood samples taken for further immunological analyses.

1. Lymphocyte-dependent responses 7 days after influenza vaccination
2. The induction of innate immune memory 14- and 42-days post-randomization

For the lymphocyte analyses, 10 participants from groups 1-3 will have blood drawn on day 21, exactly 7 days after influenza vaccination. We will assess the effect of the different treatment combinations on the response to the influenza vaccine, examining activated

influenza antibody-secreting B-lymphocytes. Due to the different timing of the influenza vaccination, participants from group 4 are not part of this analysis.

For the trained immunity analyses, 15 participants from each group will have extra blood samples taken on day 0, 14, and 42. Peripheral blood mononuclear cells (PBMCs) are isolated from the samples and subsequently stimulated in vitro with various antigens. The immune function will be assessed by cytokine production capacity measured by Luminex technology after stimulation. The outcome measure for this analysis is concentration of different types of cytokines produced following stimulations. We will compare fold change in cytokine production between the groups at the various timepoints with and without adjustment for responses in control medium. This will allow us to determine whether BCG in the different combinations with influenza vaccine induces trained immunity in this population.

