### **Secondary outcomes**

Secondary outcomes are verified SARS-CoV-2 infection (first event), self-reported respiratory infection, and all-cause hospitalization (first event). Information on positive test results will be retrieved from the Danish Health Data Authority (Sundhedsdatastyrelsen) and information on self-reported respiratory infections will come from the follow-up questionnaires.

Verified SARS-CoV-2 infection is defined as having a positive SARS-CoV-2 PCR (Polymerase Chain Reaction), rapid antigen test, or converting from negative to positive antibody test (IgG positive) without having been vaccinated.

Self-reported illness is defined as a respiratory infection if the participants report having had a respiratory infection such as common cold, influenza, pneumonia or similar term, or they report having had one or more of the following symptoms: cough, sore throat, runny nose/nasal congestion (common cold symptoms), loss of smell or taste sense, or dyspnea with or without general symptoms such as fever, chills, muscle ache, headache, and fatigue (dyspnea only if in combination with fever).

All-case hospitalization (first event) will include all hospital contacts with duration of 24 h or more, to ensure we only include hospital admissions and not visits to outpatient clinics.

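### Part B counts fever alone as a self-reported infection even in the survey periods that open on injection days, so vaccine fever can be scored as infection unequally across arms, mainly in the day 0-14 analysis

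*SAP*

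**What the plan says.** All references are to the SAP, Part B unless stated.

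- **Definition (section 13.0, Secondary outcomes).** The first criterion is "Having one or more of the following symptoms: fever, cough, sore throat, runny nose/nasal congestion (common cold symptoms"), followed by loss of smell or taste, vomiting and diarrhea. One item is enough. The second criterion is "Having dyspnea AND fever with or without general symptoms". The third is an infectious cause named by the participant.
- **How the criteria combine (same section).** "Disease episodes are characterized as infections if participants report symptoms compatible with an infectious disease or they report an infectious disease diagnose" as the cause. Participants do name a cause ("Furthermore, we ask them to provide the most likely cause for their illness"), but the answer can only add an infection. It cannot remove a fever that the participant puts down to the injection.
- **Injections and surveys (section 10.0, Trial design).** "Participants are vaccinated once at day 0 and twice at day 14 (one shot in each arm"). "Every survey period is 14 days, starting from day 0 (inclusion"). A survey period therefore opens on each injection day.
- **Analysis periods (section 13.0).** "Baseline for analysis is set at day 14 reflecting completion of the allocated vaccinations", and a further analysis covers days 0 to 14.
- **Event handling (section 14.0).** An event is dated to the first day of its survey period, and the following 14 days leave the risk set.
- **Adverse events (section 15.0, Table 4).** Fever has its own row, next to injection site reaction, fatigue and headache.

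**The concern.** A short fever after an injection, reported as illness with nothing else, satisfies the infection definition and can also appear in the adverse-event table. Because the injections differ by arm on both days, any fever they cause is a consequence of allocation. Randomization does not balance it. The SAP has no washout after injection, no exclusion of fever attributed to vaccination and no sensitivity analysis on this point.

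At stake is the reading of the Part B clinical outcome. Reactogenicity could appear as an excess of infections in an arm given an active injection, or could hide a real reduction. A scored fever also uses up the one event allowed per survey period, so a true infection in that period adds nothing.

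**Working it through.** The plan states no figure for this point, so there is none to reproduce. The check has two parts.

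**1. Which contrasts are exposed (schedule in section 10.0)**

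| Period | Group 1 | Group 2 (control) | Group 3 | Group 4 |
|---|---|---|---|---|
| Opens day 0 | BCG | Placebo | Placebo | IIV |
| Opens day 14 | IIV + placebo | IIV + placebo | IIV + BCG | Placebo + BCG |

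- Day 0-14 analysis: Groups 1 and 4 each had an active shot against placebo, so both are exposed. Group 3 versus 2 is placebo against placebo and is not. Only Group 1 has had BCG by then.
- Analysis from day 14, Group 1 versus 2: the shots are identical, so the day-14 injections create no difference.
- Analysis from day 14, Group 3 versus 2: BCG is added to the same IIV, so extra fever counts against BCG.
- Analysis from day 14, Group 4 versus 2: one active shot replaces another. The net effect is zero if BCG and IIV cause equal fever and of unknown sign otherwise.

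**2. Size under assumed rates**

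Assumptions, because the SAP gives neither rate:
- p = true infection risk per 14-day period, 5-10%;
- f = excess fever without another qualifying symptom in the exposed arm, 2-5 points, in one period only;
- no true effect of BCG.

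Single injection period: apparent risk ratio = [p + (1 − p)f] / p.

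Six-month analysis: taking six months as 182 days, (182 − 14)/14 = 12 periods, of which one follows an injection. Apparent ratio = [12p + (1 − p)f] / 12p.

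| p | f | One injection period | Twelve periods |
|---|---|---|---|
| 5% | 2% | 0.069/0.05 = 1.38 | 0.619/0.60 = 1.03 |
| 5% | 5% | 0.0975/0.05 = 1.95 | 0.6475/0.60 = 1.08 |
| 10% | 2% | 0.118/0.10 = 1.18 | 1.218/1.20 = 1.02 |
| 10% | 5% | 0.145/0.10 = 1.45 | 1.245/1.20 = 1.04 |

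Removing 14 days of risk time per event hardly changes the twelve-period figures (1.017 to 1.084).

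In people, with 75 per group (section 10.0, Sample size), the extra events number 75(1 − p)f. This runs from 75 × 0.90 × 0.02 = 1.4 to 75 × 0.95 × 0.05 = 3.6, against 75p = 3.8 to 7.5 true infections in the period.

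If there were a true ratio of 0.75 (an illustration, borrowed from the 25% reduction hypothesized in Part A), the same assumptions give 0.94 to 1.71 in the injection period and about 0.77 to 0.83 over twelve periods.

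**The case against.** The strongest case against is that this is a small matter in a secondary outcome.

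- **Dilution and power.** Over six months the distortion is a few percent, and section 10.0 already says that only pronounced clinical differences could be shown. This stands for the main analysis. It does not cover the day 0-14 analysis, which consists of a single injection period and has no dilution.
- **Filters before scoring.** Participants are first asked whether they were ill, and the questionnaires also ask about side effects. Some mild fevers may never be entered as illness. This is fair and limits the size, but it is not a rule against scoring vaccine fever.
- **Time zero.** An event dated to day 14 falls at the start of the main analysis. The SAP does not say how such an event is handled, and some handling would drop it. This too may shrink the effect in the main analysis.
- **Fever is a natural sign of infection.** Part A mentions fever only as an accompaniment ("with or without general symptoms such as fever, chills, muscle ache, headache, and fatigue"), but it defines respiratory infection, a narrower outcome, so the contrast does not prove a fault. Better internal evidence is that the dyspnea-and-fever criterion is redundant when fever alone already qualifies.

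A reader might infer more than the documents support. One inference is that every BCG group is biased against BCG; the schedule shows a predictable direction from day 14 only for Group 3. Another is that the single-period ratios describe the six-month hazard ratios; they do not. A third is that Table 4 establishes fever as a vaccine reaction. That table also has rows for infection and for death from any reason, so it shows only that fever is counted there too.

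**Conclusion.** The concern holds, with limited scope. Followed as written, the plan would score post-injection fever reported as illness as infection, unequally across arms. The additional day 0-14 analysis is the one materially distorted: for Groups 1 and 4 against control, the risk ratio under no effect would be about 1.18-1.95. In the main analysis, Group 3 versus 2 would be shifted by about 1.02-1.08 against BCG, Group 4 versus 2 in an unknown direction, and Group 1 versus 2 not at all by the day-14 shots.

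These sizes rest entirely on the assumed 5-10% infection risk and 2-5 points of excess fever, and on that fever being reported as illness and retained in the analysis. The antibody primary outcome and the analysis of infections after day 42 by antibody level are not affected.

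**What to change.** Add a rule to the self-reported infection definition in Part B, section 13.0. For the survey periods day 0-14 and day 14-28, identically in all four groups, fever counts as an infection only when accompanied by at least one of:

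- another qualifying symptom of the first criterion (cough, sore throat, runny nose or nasal congestion, loss of smell or taste, vomiting, diarrhea);
- dyspnea;
- a reported infectious cause.

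The rule should say explicitly that the general symptoms (such as headache, myalgia and fatigue) do not suffice. Otherwise fever with headache and fatigue, all three of them Table 4 rows, would still be scored as infection. Fever that does not meet the rule stays in Table 4.

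If the main definition is to remain unchanged, the minimum is a prespecified sensitivity analysis using this rule, for both the day 0-14 analysis and the analysis from day 14.

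The cost is a short addition to the text and a coding rule. Symptoms and perceived cause are already collected. The downside is that a few true fever-only infections in the first four weeks go uncounted, under the same rule in every arm.

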#### Secondary outcomes:

##### *Self-reported infections:*

The hazard ratio of infections will be estimated using an Andersen-Gill Cox proportional hazards regression model with infections included as recurrent events and time since inclusion as underlying time scale. The proportional hazards assumption will be tested using Schoenfeld residuals. As participants are only able to report one infectious episode during a follow-up questionnaire, the event will be assigned to the first day within the questionnaire period, and the following 14 days of follow-up excluded for analyses as it represents risk free time.

Association between influenza antibody titer level at day 42 and rate of infections will also be explored in Andersen-Gill Cox proportional hazards regression model, using antibody titer at day 42 as exposure and self-reported infections after day 42 as outcome. Antibody titers will be categorized into quartiles or similar relevant categories. The analysis will be adjusted for sex and age group.

Absolute risk reduction will be calculated using Cox regression.

*Immunological outcomes (subgroup analyses):*

Mean change in number of activated B-cells, concentration of cytokines, as well as fold change in cytokine concentration after stimulation from day 0 to day 14 and from day 14 to day 42 will be compared between the control group and the three treatment groups in linear regression analyses. With and without adjustment for responses in the control condition.

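### Part B immunology subset is called random but is made up of the first to accept, and its models omit the stratification factors that the primary models include

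*SAP*

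**What the plan says.** All of this concerns Part B of the SAP.

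- **Selection (13.0, Secondary outcomes).** "A random subset of participants (the first to accept) have extra blood samples taken for further immunological analyses".
- **Size (13.0).** For the lymphocyte analysis, "10 participants from groups 1-3 will have blood drawn on day 21". For the trained-immunity (cytokine) analysis, "15 participants from each group will have extra blood samples taken on day 0, 14, and 42".
- **Randomization (10.0).** Allocation is 1:1:1:1, in blocks of varying size from 6 to 8, stratified by sex and by age group (65-74; 75+).
- **Primary models (14.0).** Change in antibody titer is compared "in linear regression analyses with adjustment for baseline level of GMT, age group, and sex". The logistic model for seroconversion is adjusted for age group and sex.
- **Immunology models (14.0, Secondary outcomes).** Change in B-cells, cytokine concentration and cytokine fold change "will be compared between the control group and the three treatment groups in linear regression analyses". The only adjustment named is "With and without adjustment for responses in the control condition".
- **General rule (14.0, Methods).** All analyses are done for everyone together and also stratified by sex and age group.

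**The concern.** The selection sentence contradicts itself. A random subset is drawn by a chance mechanism from those eligible, whereas the first to accept are early and willing participants. If the word is carried into a report, it misdescribes how the subset was formed.

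The model specification raises a separate question. The SAP treats sex and age group as important enough to stratify on and to adjust for in the primary models, and its background rests on immune function declining with age. Yet some of the smallest randomized comparisons in Part B, where a chance difference in sex or age composition is most likely, leave both factors out. At stake is the precision and readability of the cytokine and B-cell contrasts. These are the only direct test of the mechanistic hypothesis in the Objectives section (hypothesis b).

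**Working it through.** The SAP states no power, effect size or standard deviation for the immunology subset, so it has no figure to reproduce. The check has four steps.

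**1. Wording.** Section 13.0 gives one selection rule, first to accept, with target numbers by group. No sampling frame or random draw appears anywhere in the SAP. The rule therefore describes consecutive volunteers.

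**2. Can the stratified presentation replace adjustment?** Sex by age group gives 2 × 2 = 4 strata. The average number per arm per stratum is 15/4 = 3.75 for cytokines and 10/4 = 2.5 for B-cells (reading 10 as per group). Split by one factor only, it is 7.5 or 5. Stratified results are also separate subgroup estimates rather than one adjusted contrast, and the primary models carry explicit adjustment in addition to the same general rule. So it cannot.

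**3. How likely is a sizeable sex imbalance?** Take a difference of at least 4 women between a BCG arm and control, 15 per arm (4/15 = 27 percentage points).

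*Limit with no effect of stratification.* With X and Y independent Binomial(15, 0.5), P(|X − Y| ≥ 4) = 0.200. For at least one of three BCG arms against a shared control, sum over control counts c: Σ P(C = c)·[1 − (1 − p_c)³] = 0.433, where p_c = P(|X − c| ≥ 4).

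*With stratified blocks.* Simulation of first-to-accept quotas of 15 per arm. Assumptions, none of them SAP figures except where noted: 50% women; 30% aged 75 or over; blocks of 8 (the size within the SAP's 6-8 range that divides by four); acceptance unrelated to arm.

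| Acceptance rate | One comparison | Any of three |
|---|---|---|
| 100% | about 0% | about 0% |
| 75% | about 2% | about 6% |
| 50% | about 8% | about 19% |
| 25% | about 15% | about 33% |
| No effect of stratification (limit) | 20% | 43% |

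Repeat runs moved these by a point or two. Acceptance of 25% is a sensible lower end: with 300 participants it yields 300 × 0.25 / 4 = 18.75 acceptors per arm on average, not far above the 15 needed.

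**4. Cost in degrees of freedom.** Sex and age group are both two-level, so two parameters are added. Residual degrees of freedom before adding them, with group as the only other term:

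- Cytokines: 4 × 15 − 4 = 56, falling to 54.
- B-cells, if 10 means per group (groups 1-3): 30 − 3 = 27, falling to 25.
- B-cells, if 10 means in all: 10 − 3 = 7, falling to 5.

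The version that also adjusts for the control condition starts one lower in each case.

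**The case against.** Five things can fairly be said on the other side.

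- **Chance imbalance is not bias.** If acceptance is unrelated to arm, the unadjusted comparison is valid and its confidence interval already allows for chance imbalance. This stands. The case for covariates is precision and agreement with the randomization.
- **Stratified blocks already protect the subset to some degree.** This stands too. The 20% and 43% figures are a limit, and with high acceptance the imbalance risk is close to nil.
- **The model is not an outlier among secondary outcomes.** The randomized comparison of self-reported infections in section 14.0 also names no adjustment for sex or age group. True, but that comparison uses the whole trial, so chance imbalance matters less there.
- **Change and fold change remove differences in level.** This is a partial safeguard for cytokines, though not against a response that itself differs by age or sex. For B-cells the lymphocyte draw is described at day 21 only.
- **Section 14.0 already promises results by sex and age group.** At 2.5 to 3.75 people per arm per stratum this offers little.

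A reader might go further and infer that early acceptance biases the arm comparisons, because the design is "A single-blinded, placebo controlled, randomized clinical trial, with nested immunological studies" and the targets are set by group. The SAP does not support that. It does not say that acceptance follows knowledge of allocation, the cytokine subset needs a day-0 sample, and the timing of sub-study consent is commonly left to the protocol, which is not shown. Nor does the sentence "This will allow us to determine whether BCG in the different combinations with influenza vaccine induces trained immunity in this population" clearly claim more than it should: it can be read as naming the age group studied, in a trial that is voluntary throughout.

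**Conclusion.** Two limited points hold. The subset is not random as described, and the word should be removed. The cytokine and B-cell models omit the two stratification factors that the primary models include, and the stratified presentation does not make up for it at this size. Selection bias in the arm contrasts has not been shown.

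How much adjustment helps depends on the acceptance rate, which the SAP does not give. Under the assumptions above, the chance of a difference of at least 4 women at 15 per arm runs from about 0% to about 15% per comparison, and from 0% to about 33% for any of three. If stratification had no effect, the figures would be 20% and 43%. The outcomes are secondary and mechanistic and the primary antibody conclusion is untouched, so this is a minor improvement.

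**What to change.** 1. In section 13.0, delete the word random and describe the subset as the first consenting participants in each group.
2. In section 14.0, add sex and age group as covariates to the cytokine linear models, giving as the reason that randomization was stratified on them.
3. State whether the lymphocyte sample is 10 per group or 10 in all. If per group, add the same two covariates to the B-cell models. If 10 in all, keep the B-cell analysis unadjusted, because two covariates would take 2 of only 7 residual degrees of freedom.

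The cost is a few words of SAP text and two covariates already recorded for randomization, with no new samples. In degrees of freedom it is 2 of about 56 for cytokines and 2 of about 27 for B-cells at 10 per group. A table of subset baseline characteristics by arm would help readers but is optional.
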